Assessment of the effect of treatment will be based on a non-randomized, open-labeled, prospective study of intravenously administered Omegaven[®] fat emulsion to determine safety and preliminary efficacy in the treatment of PN associated liver injury. This treatment group will be compared to a group based on historical controls, i.e., a subset of patients (those whose direct bilirubin levels was ever > 2 mg/dL) previously studied by Andorsky et al.(31) This study included neonates treated between 1986 and 1996 who depended on parenteral nutrition for at least 90 days after surgical therapy for congenital or acquired intestinal diseases. Our study will primarily follow the patients included in Andorsky et al. study from 2 months before direct bilirubin first reached a level > 2 mg/dL (baseline date) until 2 months after patients either reached 3 consecutive bilirubin levels \leq 2 mg/dL or reached one bilirubin level \leq 2 mg/dL and were weaned from PN died, or underwent a liver transplant. In our exploratory analyses, we will include the entire available follow-up time in Andorsky et al. dataset for each patient.

b. Patient Selection and Inclusion/Exclusion Criteria

Omega-3 Fat Emulsion (Omegaven[®])

After the diagnosis of PNALD is made, patients who are followed by the Clinical Nutrition Service (CNS) or General Surgery Program, in conjunction with the patient's primary physician, will contact [name] or [name] and an evaluation will be performed. Cases may also include referrals of patients with PNALD from other healthcare facilities or self-referrals. If the patient's parents or guardians agree to participate in the study, informed consent will be obtained. The history of present illness and past medical history will be reviewed with the guardian and pertinent demographic and medical information will be recorded on data collection forms. This form will be used to record all laboratory results, nutritional history, and descriptions of any liver biopsies performed.

Though most patients receiving parenteral nutrition do not develop end stage liver disease, there is a small percentage of patients, typically infants and children on prolonged courses of parenteral nutrition, who do go on to develop fulminate liver failure. The study population of this protocol is limited to patients felt to fulfill any one of the following conditions:

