- a) The patient will be PN dependent and at risk for significant hepatic injury due to prolonged use of parenteral nutrition.
- b) Have significant hepatic dysfunction due to parenteral nutrition despite utilization of all conventional therapies.

Inclusion Criteria:

1. Patients will be PN dependent (unable to meet nutritional needs solely by enteral nutrition) and are expected to require PN for at least another 30 days
2. Patients considered eligible for study participation must have parenteral nutrition associated liver disease (PNALD) as defined as a direct bilirubin of ≥ 2 mg/dl or currently on Omegaven through another protocol. Other causes of liver disease should be excluded. A liver biopsy is not necessary for treatment.
3. Direct bilirubin > 2.0 mg/dl, or already on Omegaven through another protocol.
4. Signed patient informed consent.
5. The patient must have utilized standard therapies to prevent the progression of his/her liver disease including surgical treatment, cyclic PN, avoiding overfeeding, reduction/removal of copper and manganese from PN, advancement of enteral feeding, and the use of ursodiol (i.e., Actigall[®]).

Exclusion Criteria:

1. Pregnancy
2. Other causes of chronic liver disease (Hepatitis C, biliary atresia, and alpha 1 anti-trypsin deficiency,)
3. Enrollment in any other clinical trial involving an investigational agent (unless approved by the designated physicians on the multidisciplinary team)
4. The parent or guardian or child unwilling to provide consent or assent

In rare instances, patients diagnosed with PNALD may later be found to have liver disease due to other causes in addition to the use of PN (i.e., inborn errors of metabolism, viral infections). Such causes may not be known at the time of enrollment and will not preclude them from continuing in the study. For the sake of statistical analysis, however, these patients will be excluded although all data will be collected and reviewed.

Screening Procedures

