Generally, primary safety analyses will be based on time from baseline or 30 days after baseline until two months after patients first reached direct bilirubin levels $< 2\text{mg/dL}$. Baseline will be defined as information collected at the date that treatment starts for Omegaven[®] patients and on the date that patient reached bilirubin levels > 2 for soybean oil fat emulsion patients. Information on mortality and transplant will be collected during the whole treatment with Omegaven[®] and during the whole period for which we have data available in the Andorsky et al. dataset. Primary efficacy analysis will include time from baseline until the patient normalizes bilirubin (presents three consecutive direct bilirubin $\leq 2\text{ mg/dL}$ or a direct bilirubin $\leq 2\text{ mg/dL}$ and weaned from TPN). With exploratory purpose, we will also describe the curve of the several markers for the entire period that Andorsky et al. recorded data.

Outcome/Endpoints

1. Treatment safety

Our primary outcome for treatment safety will be based on patient's essential fatty acid profile. We will compare patients before treatment with Omegaven[®] started and after treatment started (one month after treatment started until treatment stopped) with respect to the frequency with which triene/tetraene ratio > 0.2 at any time. We will also compare the occurrence any event of of hypertriglyceridemia (serum triglyceride $> 400\text{mg/dL}$) between Omegaven[®] and soybean oil fat emulsions. Primary analyses for these and all other safety outcomes will be based on a follow-up time for Omegaven[®] and soybean oil fat emulsions starting 30 days after baseline, i.e., 30 days after treatment started for Omegaven[®] patients and 2 months after the first direct bilirubin level $< 2\text{ mg/dL}$ was recorded. We will also explore comparisons including the time from baseline until the end of follow-up period.

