We will also compare nutritional outcomes of the two groups including difference in weight-for- age Z-scores and height-for-age Z-scores from baseline to the moment in which the child starts enteral feeding and to the moment in which the child receives less than 10% of their calories from PN. Comparison between study groups will be performed via t-test or Wilcoxon tests, as appropriate. Using linear regression, we will explore adjustment for baseline alternative predictors of interest. Trends over time in Z-scores will also be explored using regression with repeated measure methods.

Analysis of Efficacy of Omegaven®

The primary outcome to gain preliminary evidence of efficacy will be based on the time from baseline to normalization of bilirubin level, i.e, first time point among three consecutive in which bilirubin is < 2 mg/dL. We do not anticipate that any subject will present a rebound on direct bilirubin after normalization. However, we will describe the cohort with respect to the frequency of rebounds in bilirubin levels.

Crude comparisons of time to normalize direct bilirubin levels between Omegaven® and soybean oil fat emulsion patients will be based on Kaplan-Meier curves and log-rank tests. We will estimate hazard ratios and adjust for potential baseline confounders using Cox-proportional hazard models. For all survival analysis based on non-parametric or semi-parametric methods, we will attribute an infinite time to event (i.e., time to event larger than the largest follow-up time in the whole study population) for subjects who die or receive a liver transplant before bilirubin is normalized. Subjects who die before their bilirubin levels normalize (particularly due to liver failure) have in fact the worse outcome (infinite time to normalize bilirubin) and were not censored before reaching the endpoint of interest. Results of these analysis will be compared with results of analysis excluding subjects who die or are transplanted. Time to reach a total bilirubin of 1.2 will also be compared using survival analysis methods. Analysis of this outcome will proceed as described for direct bilirubin.

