Outpatient/on Omegaven®	Direct bilirubin ≥ 2 mg/dL	PN profile, AST, GGT, CRP, lipid Panel, PT, PTT, INR, fibrinogen, EFA Panel	Weekly
	Direct bilirubin ≤2mg/dL	PN profile, AST, GGT, CRP, lipid Panel, PT, PTT, INR, fibrinogen, EFA Panel	Monthly until off Omegaven and at least 1 direct serum bilirubin < 2 mg/dL

*minimum requirements, may be performed more frequently for routine clinical care

If under the discretion of the principal investigator the patient is able to return home and receive Omegaven®, the patient is required to return to Boston every 2 months or other mutually agreed upon schedule for evaluation and follow up. The Principle Investigator also requires for arrangements to be made through the patient's home health care agency for the required weekly or monthly blood draws the patient will need while at home in order to remain on Omegaven®. The lab results then must be faxed to Children's Hospital Boston in a timely manner. Additionally, measures will be taken to decrease the chance of administration errors when Omegaven® is given in the home. Families will be provided with a letter outlining strategies for reducing medication administration errors, such as independent double-checks. Also, families will be provided with fish stickers to be affixed to their Omegaven® pump to decrease the likelihood of using the incorrect pump to administer Omegaven®.

Dose reduction will occur if there is evidence of lipid intolerance (serum triglycerides > 200mg/dL) or evidence of bleeding. Growth indices include weight, length, and head circumference will also be monitored.

Other standard care laboratory results will be captured for the Omegaven® protocol. These are listed along with the standard schedule in Table 3.

The frequency of laboratory monitoring may be reduced to monthly or as clinically necessary, for patients who have been on a stable regimen of Omegaven® for a minimum of 4 months and whose serum bilirubin and hepatic enzymes have normalized.

The CAIR team completes rounds every Wednesday morning on all inpatient short bowel patients which incorporates all Omegaven® study patients. A complete comprehensive case review for all inpatients receiving Omegaven® therapy under the compassionate-use protocol and any outpatients issues are discussed among the CAIR team and with [name], [name], and the Omegaven® study nurses. All pertinent medical, nutritional, and psychosocial outpatient information is reviewed during these case reviews.

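### If the weaning route to bilirubin normalization is kept, one unconfirmed value at or below 2 mg/dL counts, with no tie to weaning and no event date

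*Combined protocol and SAP*

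**What the plan says.** Section e introduces the primary efficacy endpoint thus: "Primary efficacy analysis will include time from baseline until the patient normalizes bilirubin (presents three consecutive direct bilirubin" values at or below 2 mg/dL. It then adds an alternative: one value at or below 2 in a patient "weaned from TPN). With exploratory purpose, we will also describe the curve of the several markers". The study-design paragraph before section b uses the same alternative to close primary follow-up for the historical controls: three consecutive low values, or one value at or below "2 mg/dL and were weaned from PN died, or underwent a liver transplant".

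The analysis plan differs. Section 5c, Analysis of Efficacy, dates normalization at the "first time point among three consecutive in which bilirubin is < 2 mg/dL". It has no weaning route and uses a strict inequality.

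The same cut-off governs entry. For Omegaven patients, section b, criterion 3 reads "Direct bilirubin > 2.0 mg/dl, or already on Omegaven through another protocol", while criterion 2 also admits a value of exactly 2. Follow-up for the historical controls starts at the first recorded value above 2.

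The laboratory schedule in section 5f, marked as a minimum, runs outpatient testing at the lower bilirubin level "Monthly until off Omegaven and at least 1 direct serum bilirubin < 2 mg/dL". Inpatients off Omegaven have one complete set listed. Section 5c plans only to describe rebounds; they do not cancel or redate an event.

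**The concern.** The three-value route has confirmation built in. The weaning route drops it and puts nothing in its place. The text does not say whether the low value must fall before, at or after weaning, within what window, whether it must be the latest value, or which date enters the Kaplan-Meier and Cox analyses.

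A hypothetical record shows the consequence: 3.0, 2.6, 1.9, 2.8, 3.1, with weaning at 3.1. Under the stated rule this patient has normalized, possibly at the third visit, although the latest values are above 2. Because entry and endpoint share a cut-off, patients whose true level sits just above 2 are the most exposed. The comparison is non-randomized, and sampling intensity and starting levels may differ between groups, so a rule sensitive to chance dips adds an avoidable uncertainty to the primary result.

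**Working it through.** **No figure to reproduce.** The documents give no power, effect size or bilirubin variability for this endpoint. What follows is illustration under stated assumptions.

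**Direction.** With the alternative, the event occurs when either route is first satisfied. For the same inequality, its date can therefore only equal or precede the date under three consecutive values alone, and the set of events can only grow.

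**Inputs.** The threshold of 2 mg/dL is from section e. Weekly sampling above 2 on Omegaven is from section 5f, and two-week abstraction in the original controls from section f, Data Collection Methods. Over an assumed 12 weeks these give k = 12 and k = 6 samples. Also assumed: a constant true (median) level T, independent log-normal variation with coefficient of variation CV, and recording to 0.1, so that a recorded value at or below 2.0 means a value below 2.05.

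**Formulas.** σ = √ln(1 + CV²); p = Φ[ln(2.05/T)/σ]; chance of at least one low value = 1 − (1 − p)^k. The chance of a run of three comes from a recursion on the current run length.

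**Example, T = 2.5, CV 15%.** σ = √ln(1.0225) = 0.149; ln(2.05/2.5) = −0.198; p = Φ(−1.33) = 0.092. Then 1 − 0.908^6 = 44% and 1 − 0.908^12 = 68%.

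| T (mg/dL) | CV | One given value low (p) | At least one, k = 6 | At least one, k = 12 | Run of three, k = 6 / 12 |
|---|---|---|---|---|---|
| 2.2 | 15% | 32% | 90% | 99% | 10% / 22% |
| 2.5 | 10% | 2.3% | 13% | 25% | under 0.1% / under 0.1% |
| 2.5 | 15% | 9.2% | 44% | 68% | 0.3% / 0.7% |
| 2.5 | 20% | 16% | 64% | 87% | 1.4% / 3.4% |
| 3.0 | 10% | under 0.1% | under 0.1% | 0.1% | under 0.1% / under 0.1% |
| 3.0 | 15% | 0.5% | 3% | 6% | under 0.1% / under 0.1% |
| 3.0 | 20% | 2.7% | 15% | 28% | under 0.1% / under 0.1% |
| 4.0 | 20% | under 0.1% | 0.2% | 0.4% | under 0.1% / under 0.1% |

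Without rounding (cut at 2.00), the T = 2.5, CV 15% row gives 34% and 57%. Each figure is the chance of a qualifying dip; the patient must also be weaned to become an event.

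**Event date.** Simulated patients (20,000 per setting, weekly values, no rounding, assumed median time to weaning 16 weeks) had a true fall from 3 mg/dL with a 12-week half-life, so the true level crosses 2 at 12 × log₂(3/2) = 7.0 weeks. With CV 20%, the median event time is 9 weeks on three consecutive values, 8 weeks if dated when low value and weaning both hold, and 6 weeks if dated at the first low value. With CV 10% these are 8, 8 and 7 weeks. For a fall from 6 with an 8-week half-life and CV 10%, all three are 13 weeks.

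**Between groups.** At the same true level of 2.5 and CV 15%, weekly sampling gives more dips than two-weekly (68% against 44%). But a control at 2.2 sampled two-weekly has a 90% chance, against 6% for an Omegaven patient at 3.0 sampled weekly. Controls start at their first value above 2, and the plan expects Omegaven patients to be sicker, so the second contrast is as plausible as the first.

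**The case against.** The strongest reply is that section 5c, the analysis plan proper, omits the weaning route; if that text governs, the problem never reaches the primary analysis. This stands as a condition on the point. It does not dispose of it, because the route appears in the endpoint-definition section and in the study-design paragraph.

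A second reply is that the natural reading places the low value around weaning, which the outpatient laboratory row supports. That is a fair guess at intent, and on a last-value reading the T = 2.5, CV 15% figure falls to 9%. But the laboratory row does not define the endpoint, and neither statement of the route gives an order or a date.

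Two stronger readings are tempting. A reader might infer that weekly sampling biases the result towards Omegaven. The documents do not support that: starting levels pull the other way, two-week spacing is stated only for the original controls, and the contemporary controls must have two consecutive values of at least 2.0 and have no stated spacing. A reader might also take the percentages as expected false events in this study. They are not: variability and true levels are assumed, weaning is not modelled in the table, and correlated values would change the contrast with runs of three.

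**Conclusion.** The point holds conditionally. If the weaning route survives reconciliation with section 5c, a transient dip followed by weaning at a raised level is a primary event under the stated rule, and its date is undefined. The direction relative to three consecutive values is certain: more events or earlier dates, never the reverse. The size is not known. Under the constant-level model it could be substantial for true levels near 2 to 2.5 mg/dL, depends heavily on the CV at 3.0, and is negligible at 4.0. The net effect on the comparison of Omegaven with controls cannot be signed from the documents. This is worth correcting before analysis, mainly because doing so needs little more than wording.

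**What to change.** Use one endpoint definition, with one inequality, in the study-design paragraph, section e and section 5c. If the weaning route is kept:

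- Require that the last direct bilirubin on or before the weaning date is at or below 2 mg/dL. If it is not, date the event at the first later value at or below 2; without such a value there is no event by this route.
- Date the event no earlier than weaning.
- Define weaned for analysis purposes. The Duration of Therapy text lets Omegaven continue after the dextrose/protein portion of PN stops, so the weaning date is otherwise ambiguous.
- Add a sensitivity analysis that counts only three consecutive values.

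Do not make a post-weaning value, or the absence of later rebound, a condition of the primary event. The minimum two-month follow-up is specified for Omegaven patients, whereas control records are fixed, post-PN follow-up was only typical for at-risk controls, and the plan itself expects more missing control data. Such a condition could remove control events preferentially. Report post-weaning confirmation and rebound descriptively by group instead.

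The cost is that some events are dated later or lost, and one more analysis is run. The repaired rule still rests on a single value, so some noise remains (9% for the last value at T = 2.5, CV 15%, before any later values are considered); the sensitivity analysis shows whether that matters. No extra visits or tests are needed.

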Additional comparisons across treatment periods for subjects receiving Omegaven® will be aimed to assess occurrence of spontaneous bleeding (e.g., unexplained bruising, oozing from gums/incision sites), and maximum triene/tetraene ratio, minimum platelets, and maximum international normalized ratio (INR), trends in pre-albumin (age standardized levels). We will also explore trends in coagulopathies based on curves of platelets, prothrombin time (PT), partial thromboplastin time (PTT) over time, and INR. We will also describe the rate with which INR ratios were > 2 (number of days/follow-up time), as a marker of coagulopathies.

Additional comparisons between Omegaven® and soybean oil fat emulsion groups will be performed with regards to rate in which albumin is > 3 g/dL, maximum triglyceride level, rate of blood stream infections (number of positive blood cultures/follow-up-time under PN after baseline), rate of central venous catheter (CVC) infections (number of CVC infections/follow-up time and number of gram positive CVC infections/follow-up time), and occurrence of anaphylactic reactions after baseline.

Nutritional outcomes between Omegaven® and soybean oil fat emulsion groups that will be compared include changes in weight- and height-for-age Z-scores from baseline to 10% PN or cessation of PN..

We will describe trends over time for all outcomes associated with fatty acid profiles (including triene/tetraene ratios, triglycerides, total omega-6 fatty acids, total omega-3 fatty acids, total saturated, total monounsaturated, and total polysaturated fatty acids). Specific fatty acids such as arachidonic, palmoleic, palmitic, oleic, stearic, and linoleic fatty acids will also be evaluated and described. Also, for exploratory purposes, we will compare the trend in weight- and height-for-age Z-scores between both groups.

2. Omegaven®

3. The patient will complete treatment with Omegaven® in this study when he/she is completely off PN, develops a contraindication for further use, or the patient/family requests to be removed from the study.

f. Data Collection Methods, Assessments and Schedule

Omega-3 Fat Emulsion (Omegaven™)

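### The day-30 start of the primary safety window leaves first-month bleeding and triglyceride events out of the primary summary, and the documents conflict on whether it also applies to anaphylaxis

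*Combined protocol and SAP*

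**What the plan says.** **Start of the window.** Section e (Definition of Primary and Secondary Outcomes/Endpoints), under Treatment safety, introduces the triene/tetraene ratio and triglycerides above 400 mg/dL. It then sets one rule for the primary analyses, covering both of those outcomes and the rest: "all other safety outcomes will be based on a follow-up time for Omegaven[®] and soybean oil fat emulsions starting 30 days after baseline". Section 5c (Analysis of Safety and Tolerability) gives the same start twice: once for outcomes measured only in the Omegaven group and once for outcomes measured in both groups. The comparison from day 0 is secondary in standing: "We will also explore comparisons including the time from baseline until the end of follow-up period".

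**Looser wording.** Section e opens differently: "Generally, primary safety analyses will be based on time from baseline or 30 days after baseline", without assigning any outcome to either start. Its list of additional comparisons includes "occurrence of anaphylactic reactions after baseline" and defines the blood stream infection rate as "number of positive blood cultures/follow-up-time under PN after baseline".

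**Which outcomes are primary.** Section e says "Our primary outcome for treatment safety will be based on" the essential fatty acid profile, and it places spontaneous bleeding and anaphylaxis among additional comparisons. Section 5c calls both primary, together with triglycerides above 400 mg/dL and, in the Omegaven group only, INR above 2.

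**Baseline.** It is "the date that treatment starts for Omegaven[®] patients and on the date that patient reached bilirubin levels > 2" for the soybean group. The two groups therefore start their clocks at different kinds of event.

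**Exceptions.** Growth Z-scores run from baseline (sections e and 5c). Mortality and transplant are collected over the whole Omegaven treatment period (section e).

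**The concern.** A 30-day lag suits an outcome that needs time to reflect the new lipid, such as the triene/tetraene ratio. It suits acute outcomes poorly. Section 5f asks for close observation for allergic reaction at and shortly after the initial administration, and Table 2 concentrates triglyceride testing in the first four weeks. A primary window that opens at day 30 looks away from both.

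Aim 1 is the safety profile, and hypotheses 1.1 and 1.2 name triglycerides above 400 mg/dL and unexpected bleeding. The primary safety analysis is descriptive (sections 5c and 5d), so type I error is not at issue. What matters is which events the main table counts. Someone who reads only that table could take an absence of events after day 30 for an absence of events on Omegaven.

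**Working it through.** The plan gives no figure for the effect of the window, so there is none to reproduce. Its only power figures for two-group safety comparisons (Table 5) are not in dispute: for 5% versus 40%, an exact two-sided Fisher calculation gives 71.6%, 82.2% and 89.3% against the stated 72%, 82% and 89%.

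**1. What the text implies for each outcome**

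| Outcome | Start in primary analysis | Status |
|---|---|---|
| Triglycerides > 400 mg/dL | Day 30 (sections e and 5c) | Primary in 5c |
| Unexpected bleeding | Day 30 (sections e and 5c) | Additional in e, primary in 5c |
| INR > 2 | Day 30 (sections e and 5c) | Primary in 5c |
| Anaphylaxis | Day 30 by the general rule; after baseline in its own line in e | Additional in e, primary in 5c |
| Growth Z-scores | Baseline | Outside the lag |

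Section h says that patients with an anaphylactic or allergic reaction do not continue Omegaven. A first-infusion reactor therefore cannot appear in an on-treatment window that opens at day 30.

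**2. Triglyceride tests.** Table 2 requires tests weekly for four weeks after baseline, i.e. on days 7, 14, 21 and 28. All 4 of 4 precede day 30.

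**3. Share of the window left out (illustration).** Let T be the day direct bilirubin first falls below 2 mg/dL. T is an assumption; the four values are weeks 4, 8, 12 and 24. Following the opening sentence of section e, the full window runs from day 0 to T + 60. The pre-treatment test is not counted.

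- Section 5f schedule, weekly to T and then at T + 30 and T + 60: share = 4 / (T/7 + 2).
- Table 2 minimum, days 7 to 28 and then every 30 days from day 58: share = 4 / (number of tests up to T + 60).
- Person-time: share = 30 / (T + 60).

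| T (days) | Tests, 5f schedule | Tests, Table 2 minimum | Person-time |
|---|---|---|---|
| 28 | 4/6 = 67% | 4/6 = 67% | 30/88 = 34% |
| 56 | 4/10 = 40% | 4/6 = 67% | 30/116 = 26% |
| 84 | 4/14 = 29% | 4/7 = 57% | 30/144 = 21% |
| 168 | 4/26 = 15% | 4/10 = 40% | 30/228 = 13% |

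These are shares of tests and time, not of events. The documents give no early event rate.

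**4. Effect per patient.** Section 5d tabulates power for 20, 25 and 30 patients. If a patient whose only event falls before day 30 stays in the denominator, the primary proportion drops by 1/20 = 5.0, 1/25 = 4.0 or 1/30 = 3.3 points.

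**5. One early reactor (illustration).** Assume one first-infusion reaction and none later. The exact two-sided 95% upper limit for zero events is 1 − 0.025^(1/n); for one event it is the Clopper-Pearson limit.

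| n | Primary table from day 30 | From day 0 |
|---|---|---|
| 20 | 0/20, upper limit 16.8% | 1/20, upper limit 24.9% |
| 25 | 0/25, upper limit 13.7% | 1/25, upper limit 20.4% |
| 30 | 0/30, upper limit 11.6% | 1/30, upper limit 17.2% |

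The plan does not say whether the reactor stays in the denominator. If not, the first row becomes 0/19 (upper limit about 17.6%). The event is missing either way.

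**The case against.** **The lag is not universal.** A reader might infer from the general sentence that every safety outcome starts at day 30. That is too broad: growth Z-scores run from baseline, and mortality and transplant have their own collection period. The plan already varies its start by outcome. This objection stands.

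**Anaphylaxis has its own wording.** A reader might also infer that anaphylaxis is definitely excluded in the first month. The documents do not settle that. The after-baseline phrase and the either/or opening of section e point one way; the general rule in sections e and 5c points the other. For anaphylaxis the supportable claim is a conflict.

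**Early events are not lost.** Adverse events are reported from the first infusion (section h), the investigators review cases at least monthly, and the monitoring board chair receives all adverse event reports (section 5f). Section e describes triglyceride trends over time. Potential Study Limitations promises a before/after comparison of all safety outcomes in Omegaven patients and mentions no lag. So it would be wrong to say that first-month events surface nowhere but in the exploratory comparison. None of this changes what the primary summary counts.

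**A lag can be defended for two-group comparisons.** Controls enter when bilirubin passes 2, already on soybean lipid. Starting Omegaven at day 30 sets established users against established users; starting at day 0 sets new users against established ones. Early INR and triglyceride values may also reflect existing disease or prior soybean lipid. This stands, and it argues for showing both windows for those outcomes and against replacing one with the other.

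**Conclusion.** The point holds in limited form. As written, the primary descriptive summary omits first-month unexpected bleeding and triglycerides above 400 mg/dL, and starts INR above 2 at day 30. For anaphylaxis the text conflicts with itself, and the day-30 reading could not show a first-infusion reaction on treatment.

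The firm figures are that all four required weekly triglyceride tests fall outside the window, and that each patient whose only event is early lowers the proportion by 5.0, 4.0 or 3.3 points. The latter assumes the patient stays in the denominator and uses power-table sizes; section 5d says enrolment is not driven by power. The ranges of 15–67% of tests and 13–34% of person-time rest on assumed normalisation times. They do not show that any such share of events would be missed, and no effect on significance follows, because the primary safety analysis is descriptive. The matter should be fixed; it does not undermine the study's safety oversight.

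**What to change.** In sections e and 5c, state one start and one end for each safety outcome:

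- **Anaphylaxis and unexpected bleeding:** count from first infusion (day 0) in the primary summary, with every infused Omegaven patient in the denominator. Describe them mainly within the Omegaven group, and show separately the patients already on Omegaven at entry, whom the inclusion criteria allow.
- **Triglycerides above 400 mg/dL, INR above 2 and infections:** report the from-baseline and day-30 windows side by side in the primary summary.
- **Triene/tetraene ratio and other fatty-acid outcomes:** keep the 30-day lag.

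Reconcile sections e and 5c and Potential Study Limitations on the window, and sections e and 5c on which outcomes are primary and which additional. Include the clause in section e that explains the start as "30 days after treatment started for Omegaven[®] patients and 2 months after the first direct bilirubin level" below 2 mg/dL. The opening sentence of that section uses a similar phrase for the end of the window, while section 5c starts controls 30 days after bilirubin exceeds 2.

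The cost is wording only: the data are already collected and a from-baseline comparison is already planned. The downside is that some early events carried over from existing disease or prior soybean lipid will count against Omegaven; a sentence beside the table should say so.
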